3.6 Treatment assignment and treatment groups

Given that patients will be followed for 8 years, it is anticipated that patients will switch CD medications while enrolled in the registry. Therefore, a patient's treatment at registry enrollment will most likely not reflect their exposure throughout the study. Three comparisons may be used to reflect these treatment changes over time and provide context for events reported to the registry. See Section 8.1.4 for details.

Treatment start is the recording period (ie, the informed consent date). Only study emergent adverse events will be reported. Study emergent begins at the informed consent through the end of the study.

Treatment by enrollment cohort will consist of two groups:

- Cimzia
- Comparator
 - where comparator includes:
 - Corticosteroids
 - Immunosuppressants
 - Other biologics (e.g. anti-TNFs) other than Cimzia

Enrollment cohort is recorded and will be assumed regardless of the presence of prior or imputed CD medication referring to the other treatment group. These are the default treatment groups.

Some summaries will be repeated by actual treatment at Baseline to examine differences between treatment by enrollment cohort. Actual treatment at Baseline will be summarized in three groups:

- Cimzia at BL
- No Cimzia at BL
- Gap (absence of Cimzia and comparator)

Actual treatment will be used for adverse event tables unless specified otherwise. If a patient received Cimzia up to 70 days prior to baseline (half-life of CZP), the patient is a member of the treatment group "Cimzia at BL". For the calculation of the Hazard Ratio, the group 'Cimzia at BL' is compared against the combined group "No Cimzia at BL" and "Gap".

For malignancies, person-time and events will be categorized into 2 groups:

- Cimzia
- Comparator

where a patient is systematically attributed to Cimzia from their first dose of Cimzia until the end of the study, even after ending or switching from Cimzia.

For acute events, person-time and events will be categorized into 5 groups:

- Cimzia
- Comparator
- Overlap (Cimzia and comparator)
- Gap (absence of Cimzia and comparator)
- Any Cimzia (Cimzia and Overlap)

Example treatment allocations for malignancies and acute events are in Section 11.1, appendix 1.

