8.1 Statistical analysis of the primary endpoints

The primary analysis of this study is descriptive and no formal hypothesis testing will be conducted. For the primary analysis, adverse event rates will be calculated by dividing the number of reported safety events by the patient-years at risk. Cimzia-specific rates will be calculated and compared to all other CD treatment rates.

Propensity scores will be used to assess the comparability of patients who are receiving Cimzia at baseline to those who are receiving another CD medication. Appropriate analytical methodologies will be used to investigate the effect of time varying confounders.

Time-to-event analyses for each Adverse Event of Interest will be conducted using Cox proportional hazard modeling and Kaplan-Meier curves.

Analyses of specific outcomes may be conducted if appropriate.

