8.1.3 Time-to-event analysis

Time-to-event analyses will be conducted for each Adverse Event of Interest.

Please refer to Section 3.6 for the assignment of treatment groups and to Section 3.2.1 for details on exposure times.

Cimzia vs. Comparator (acute event rules)

Per patient and Adverse Event of Interest, exposure time until the first occurrence of the AE is considered. Prior to the AE, at any given time after treatment start, the patient can be exposed to either of: Cimzia, Comparator, Overlap, or Gap (one at a time but with switches between them). Thus, up to the first occurrence of the AE, 4 exposure times are recorded, one for each treatment. The first occurrence of the AE is counted as event for the actual treatment where it occurred (i.e. exactly one of Cimzia, Comparator, Overlap, or Gap), and exposure time is censored for the remaining 3 treatments. If no AE of interest occurred, time will be censored at the end of exposure for all treatments. The comparison of interest is Cimzia vs. Comparator.

Any Cimzia vs. Comparator (acute event rules)

Per patient and Adverse Event of Interest, exposure time until the first occurrence of the AE is considered. Prior to the AE, at any given time after treatment start, the patient can be exposed to either of: Any Cimzia (i.e. Cimzia monotherapy or Overlap), Comparator, or Gap (one at a time but with switches between them). Thus, up to the first occurrence of the AE, 3 exposure times are recorded, one for each treatment. The first occurrence of the AE is counted as event for the actual treatment where it occurred (i.e. exactly one of any Cimzia, Comparator, or Gap), and exposure time is censored for the remaining 2 treatments. If no AE of interest occurred, time will be censored at the end of exposure for all treatments. The comparison of interest is Any Cimzia vs. Comparator.

Cimzia vs. Comparator (malignancy rules)

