8.1.4 Incidence and event rate calculation

In general, for each, the cumulative incidence, incidence rate and corresponding 95% confidence interval will be presented. For the incidence rate, the numerator will be the total number of patients experiencing the AE of interest for the first time in the study (if a patient switches treatment and has an AE of interest it will be considered a recurrence if the AE occurred while on a previous treatment). The denominator will be in 100 patient-years. That is, the denominator will be the total summation of individual patient-years at risk up the first occurrence of the AE of interest for subjects with that AE, and the total patient-years at risk for those subjects not experiencing that AE, divided by 100. Two-sided 95% confidence intervals for the incidence rates are calculated [using the GAMINV function in SAS] to determine the upper and lower limits for the number of events for each AE of interest, which is assumed to follow a Poisson distribution, divided by the total patient-years of exposure multiplied by 100. [Note that the method to be used follows a SAS implementation using the GAMINV function and is described in detail on bottom, right hand side of p. 2 and the code in the box on the left hand side of p. 3 in the SUGI paper <http://www2.sas.com/proceedings/sugi26/p241-26.pdf>].

A Poisson AE of interest regression analysis, accounting for within-patient correlations, implemented with the GENMOD procedure in SAS, is used to test for the differences in incidence rates between actual treatment cohorts at the two-sided $\alpha=0.05$ level. Potential code for these models is:

```
PROC GENMOD data = XXXXX;  
CLASS COHORT;  
MODEL AEOFINT = COHORT / D = POISSON OFFSET = LPRSNYRS;  
RUN;
```

Where AEOFINT is the number of events for a particular AE of interest, LPRSNYRS is the log of the total number of patient-years, and COHORT represents the actual treatment cohorts. Type III analysis will be used to get the cohort effects conditional on all covariates listed above in Section 4.1.

For event rates, the numerator will be the number of AEs of interest, including repeat occurrences in individual subjects. The denominator will be the total exposure in 100 patient-years, without censoring the exposure to the first event. That is, the total summation of individual patient-years divided by 100. No confidence intervals will be computed for event rates.

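### For acute events, the SAP 8.1.4 rate test leaves the treatment levels undefined; with the SAP's acute groups it is a joint 2- or 3-df test, not a test of Cimzia versus Comparator

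*SAP*

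**What the plan says.** SAP 8.1.4 uses Poisson regression to test "differences in incidence rates between actual treatment cohorts at the two-sided $\alpha=0.05$ level". The sample code, labelled as potential code, declares COHORT as a class variable and fits "MODEL AEOFINT = COHORT / D = POISSON OFFSET = LPRSNYRS". The only definition given is that "COHORT represents the actual treatment cohorts". The result is to come from the joint effect of that factor: "Type III analysis will be used to get the cohort effects conditional on all covariates listed above in Section 4.1". No levels, reference group or contrast are named.

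The groups are set out elsewhere:

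- SAP 3.6: "For acute events, person-time and events will be categorized into 5 groups". These are Cimzia, Comparator, Overlap, Gap and a fifth, "Any Cimzia (Cimzia and Overlap", which is the union of two of the others.
- SAP 3.6 also gives actual treatment at Baseline three groups, and gives malignancies two.
- SAP 8.1.3 records four mutually exclusive exposure states for acute events and adds: "The comparison of interest is Cimzia vs. Comparator". It then repeats the analysis with Any Cimzia, Comparator and Gap, where Any Cimzia versus Comparator is of interest.
- SAP 8.1 states the registry's question: "Cimzia-specific rates will be calculated and compared to all other CD treatment rates".

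SAP 3.6 refers the reader to 8.1.4 for three comparisons, but 8.1.4 does not list them.

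**The concern.** A Type III effect of a factor with k levels is a joint test on k − 1 degrees of freedom. Its null hypothesis is that all k rates are equal. With two levels, that is the comparison the registry wants. With three or four it is a different hypothesis.

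Gap is time off all the listed drugs, and Overlap is time on Cimzia and a comparator together. Either may have a rate of its own for reasons that say nothing about Cimzia versus Comparator. A p-value below 0.05 could then come wholly from Gap or Overlap and be read as a Cimzia difference. Conversely, a real Cimzia–Comparator difference is harder to detect, because the same signal is judged against the larger critical value of a test with more degrees of freedom.

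Table 8.1 lists 12 acute event types. Its header says malignancies are also analysed under the acute rules, so that supplementary analysis is exposed too.

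**Working it through.** **Which levels?** The documents do not say, so this step is inference.

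- SAP 3.6 contrasts actual treatment with enrollment cohort, so the word "actual" points away from the two enrollment cohorts.
- SAP 8.1.3 uses actual treatment for exactly one of Cimzia, Comparator, Overlap or Gap.
- SAP Amendment 5 says the time-to-event time at risk was aligned with the exposure-adjusted incidence analyses.
- SAP 8.1.4 promises to account for within-patient correlation, which suggests several treatment rows per patient.
- Any Cimzia contains Cimzia and Overlap, so it cannot be a further level of the same factor.

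That leaves four levels (3 df), or three with Any Cimzia or with treatment at Baseline (2 df). No actual-treatment scheme defined for acute events has two levels as it stands.

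**No plan figure to reproduce.** The 0.05 is a nominal level, not a derived number. The documents give neither person-time by exposure state nor event rates, so everything below rests on stated assumptions.

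**One case by hand.** Assume 10,000 person-years split 25/40/15/20% over Cimzia, Comparator, Overlap and Gap, a base rate of 1 per 100 person-years, equal Cimzia and Comparator rates, and rate ratios of 1.5 for Overlap and 0.7 for Gap.

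- Expected events O: 25, 40, 15 × 1.5 = 22.5, 20 × 0.7 = 14; total 101.5.
- Expected events E under one common rate: 25.375, 40.6, 15.225, 20.3.
- Noncentrality = 2 Σ O ln(O/E) = 2 × (−0.372 − 0.596 + 8.788 − 5.202) = 5.24.
- Probability that a noncentral chi-square (3 df, noncentrality 5.24) exceeds 7.815 = 0.46.

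Cimzia and Comparator contribute almost nothing to the sum; Overlap and Gap drive it. Simulation of this case gives 0.461.

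**Range.** Poisson likelihood-ratio test with four levels; 100,000 simulated datasets per setting; 10,000 or 16,000 person-years; base rate 1 or 3 per 100; split 25/40/15/20% or 25% each; Cimzia rate equal to Comparator rate.

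| Rate ratio against Comparator | 3-df test rejects |
|---|---|
| All equal | 0.050–0.052 |
| Gap 0.8 | 0.095–0.352 |
| Gap 0.5 | 0.459–0.999 |
| Overlap 1.25 | 0.098–0.447 |
| Overlap 1.5 | 0.254–0.962 |
| Overlap 1.5, Gap 0.7 | 0.461–1.000 |

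With Any Cimzia, Comparator and Gap (2 df), a Gap rate ratio of 0.5 gives 0.525–1.000. A 1-df Cimzia versus Comparator test rejects in 0.045–0.053 of datasets throughout.

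**A second split, with rarer events.** Assume 3,000, 9,000, 1,500 and 4,300 person-years for Cimzia, Comparator, Overlap and Gap (total 17,800). The total is close to what 3,045 patients give over 8 years at 8% annual drop-out: 3,045 × (1 − 0.92⁸)/0.08 = 18,528 if losses fall at year end, 18,528 × 0.92 = 17,046 if at year start, average 17,787.

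| Base rate per 100 p-y | Overlap 1.5, Gap 0.7 | Overlap 1.25, Gap 0.8 |
|---|---|---|
| 0.05 | 9% | 7% |
| 0.1 | 12% | 8–9% |
| 1 | 61–62% | 24% |
| 2 | 91% | 45–46% |
| 4 | >99% | 77–78% |

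At the two lowest rates the 1-df test itself rejects in 6–7%, because the chi-square approximation is poor with so few events.

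**Power.** A Cimzia–Comparator difference with 80% power on 1 df has noncentrality (1.960 + 0.842)² = 7.849. At that noncentrality, power is 70.9% on 2 df (critical value 5.991) and 64.5% on 3 df (7.815).

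**The case against.** The best counter-argument is that SAP 8.1.4 never says COHORT has more than two levels. The propensity-score sections and 8.1.5 use cohort for a two-level variable, Cimzia or comparator; with two levels the Type III test has 1 df and the problem vanishes. For the baseline hazard ratio, SAP 3.6 merges the no-Cimzia and Gap groups, so the authors do collapse to two when they compare. This stands as a reason to word the point conditionally. It does not settle the matter: the merging rule is given only for the hazard ratio, and 8.1.4 states no such rule.

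The wanted comparison also appears elsewhere. SAP 8.1.3 gives hazard ratios with confidence intervals for both contrasts, SAP 8.1.5 gives Cimzia versus comparator rate ratios with 95% confidence intervals, and Protocol 6.4.1.2 makes Cox modelling the primary analysis for acute events. This stands, and it limits the harm. But 8.1.5 does not say how Gap and Overlap are treated, and the 8.1.4 p-value would still be reported beside the rates.

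The simulations rest on assumed splits and rate ratios and ignore covariates and within-patient correlation. That also stands. The inflation is small for rare events such as aplastic anemia or serious skin reactions if their rates are as low as 0.05 to 0.1 per 100 person-years, which is itself an assumption.

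Three stronger readings are tempting and not supported:

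- That the factor has five levels. Any Cimzia is a union, and 8.1.3 handles it as a separate classification.
- That the test rejects whenever Gap or Overlap differs. The probability depends on the size of the difference and the number of events.
- That the registry's main conclusion is at risk. Malignancy under its own rules has two groups, and the SAP (2.1.1, 4.4, 8.1) treats all testing as descriptive.

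**Conclusion.** The point holds in conditional form. SAP 8.1.4 defines neither the levels of COHORT nor a contrast. If the acute-event groups are used, its Type III p-value tests equality of three or four rates and does not answer the Cimzia versus Comparator question of SAP 8.1 and 8.1.3.

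With equal Cimzia and Comparator rates, the joint test rejects in about 10% of cases for rare events or mild differences (7–9% in the mildest rare-event settings) and in nearly 100% for common events with marked differences. A 1-df contrast stays at about 5%, or 6–7% for very rare events. The cost in power is about 9 points on 2 df and 16 on 3 df, starting from 80%. The rejection rates depend on assumed person-time, rates and rate ratios; the degrees of freedom and the power loss at fixed noncentrality do not.

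The consequence is a descriptive p-value that can be misread, not a wrong confirmatory decision. The change is worth making because it costs little and brings 8.1.4 into line with 8.1.3.

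**What to change.** In SAP 8.1.4, for analyses under the acute rules:

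1. List the disjoint levels of COHORT, and state that Any Cimzia is never entered in the same model as Cimzia and Overlap.
2. Replace the Type III p-value with two prespecified 1-df contrasts, each reported as a rate ratio with 95% confidence interval and a descriptive p-value: (a) Cimzia versus Comparator, in the model with Cimzia, Comparator, Overlap and Gap; (b) Any Cimzia versus Comparator, in a separate model with Any Cimzia, Comparator and Gap.
3. State that any omnibus p-value is not used to describe the Cimzia comparison.

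For very rare events, read the interval and p-value with the small-count caveat shown above. The two-group malignancy-rule analysis needs no change on this point.

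Cost: a few lines of SAP text and one ESTIMATE or LSMEANS statement per model; no new data.

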8.1.5 Secondary analyses of the primary endpoints

In addition to the propensity score analysis, comparisons between Cimzia event rates and all other CD treatment rates for comparator products will be examined using rate ratios and corresponding 95% CIs from conventional multivariate regression analyses. The same vector of

covariates that are included in the propensity score analysis will be also used as confounders in the conventional multivariate regression analyses. This will allow for an assessment of the robustness of study findings. Note that the interpretation of any rate ratios using conventional modeling may be hindered if there are substantial differences in the characteristics of patients between the Cimzia and comparator cohorts.

Rate ratios comparing Cimzia event rates to other frequently used CD treatments or treatment classes will also be calculated as appropriate.

The primary analysis for acute events will be stratified on incidence/prevalence use (yes/no), where incidence use is defined as only those patients who initiated treatment upon study enrollment and prevalent use is defined as those patients who were receiving treatment prior to enrollment. If sufficient power exists, further stratification based on duration of prevalent use (eg, 1-5 months, 6+ months, etc.) may be performed.

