3.2.1.2 Person-time at risk calculations for acute events

Exposure person-time at risk will be calculated for each CD treatment using the following equation:

$$\text{Last Date} - \text{First Date} + 1$$

First date is defined as the latest enrollment date or first CD treatment date after enrollment (whichever is later) or the first dose of new treatment if switching treatments. Last date is defined as the earliest of the following:

- Date of safety event of interest (for incidence rate calculations only)
- Last dose date + treatment class-specific half-life exposure for product
- Date of discontinuation, withdrawal, or data cutoff

Any gaps in exposure, as illustrated in the figure below, will be included in the gap treatment group person-time at risk calculations for acute events. Any overlap in treatment groups will be included in the overlap group person-time at risk calculations for acute events.

Figure 2: Example person-time at risk for acute events

[figure not shown]

Figure 2 presents an example of a patient's exposure history. For this example, exposure person-time at risk would be calculated as follows:

Exposure person-time = (Last treatment date + Treatment class-specific half-life) – First treatment date + 1) + (earliest of End treatment date + treatment class-specific half-life exposure, last date in study, data cutoff date) – Resume treatment date + 1).

See Section 11.1, appendix 1 for more examples of treatment allocation scenarios for acute events.

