4.5 Examination of subgroups

The primary analysis for acute events will be stratified on incidence/prevalence use (yes/no).

The impact of data from the high accruing study site #849 on key outcomes will be assessed (Clinical site closed due to significant noncompliance; reported to FDA's Division of Scientific Investigations in letter dated 29 April 2020).

If sufficient power exists, further stratification based on duration of prevalent use (e.g., 1-5 months, 6+ months, etc.) may be performed. This is described in more detail in Section [8.1.5](#).

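### Incident/prevalent status is set once at enrollment on an unnamed treatment, so after a patient's first switch it no longer shows whether the current drug is newly started

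*SAP*

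**What the plan says.** SAP 4.5 and 8.1.5 stratify the primary acute-event analysis on a yes/no indicator of incident or prevalent use. SAP 8.1.5 defines the two levels by patient. The incident level is given as "where incidence use is defined as only those patients who initiated treatment upon study enrollment". The other level depends on whether the patient was already being treated when entering the registry: "prevalent use is defined as those patients who were receiving treatment prior to enrollment". Neither section says whether *treatment* means Cimzia, the drug taken at enrollment, or any Crohn's disease drug. No rule revises the label later. Section 8.1.5 also allows a further split by duration of prevalent use.

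The analysis being stratified treats exposure as changing over time. Under SAP 8.1.3 a patient moves among Cimzia, Comparator, Overlap and Gap, "one at a time but with switches between them". Under SAP 3.2.1.2 person-time begins at enrollment or the first treatment after it, "or the first dose of new treatment if switching treatments". SAP 3.6 expects switching: "a patient's treatment at registry enrollment will most likely not reflect their exposure throughout the study".

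**The concern.** The registry admits both new starters and patients already treated for up to 12 months. Stratifying on incident use is meant to separate the early period on a drug from time in patients who have already tolerated it. That works only if the label describes the drug to which the person-time is credited. Here the label describes enrollment, while the person-time and events follow the current drug. SAP 3.6 itself says that enrollment treatment is a poor guide to later exposure.

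The analysis is descriptive, but SAP 8.1.3 reports hazard ratios, confidence intervals and exploratory p-values. Readers will take the strata as new-user and established-user results. Because *treatment* is not defined, two programmers could also build different strata from the same data.

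**Working it through.** **Step 1: apply the definitions to typical patients.** The plan gives no figure for this stratification, so the main check is of the text.

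| Patient | Label under SAP 8.1.5 | Is the current drug new? |
|---|---|---|
| Comparator, on treatment before enrollment, starts Cimzia in year 3 | Prevalent | Yes |
| Comparator, began treatment at enrollment, starts Cimzia in year 3 | Incident | Yes |
| Cimzia, on it before enrollment, later starts a comparator drug for the first time | Prevalent | Yes |
| Either cohort, changes drug at enrollment | Meets both definitions | Yes |
| Comparator, starts Cimzia in year 3, *treatment* read as Cimzia only | Meets neither definition | Yes |

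Rows 1 and 3 are misfiled. Row 2 is filed acceptably. Rows 4 and 5 have no rule. The optional split by duration of prevalent use has the same fault, since after a switch it measures time on a drug the patient has left.

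**Step 2: look for a repair elsewhere.**

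- Protocol 6.4.1.2 has a secondary Kaplan-Meier analysis censored at the first switch. It would suit an enrollment label, but SAP 8.1.5 does not list it.
- Censoring rules A and B in SAP 5.1 apply to time to discontinuation.
- The 6-month within-patient comparison after a new start in Protocol 6.2 is optional.
- SAP Appendix 1 says that dosing before consent affects malignancy time only, so the acute-event rules do not supply prior use by drug.

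**Step 3: illustrate the size.** From SAP 2.4: 1371 Cimzia patients, 1674 comparator patients, 8% annual drop-out. From SAP 3.6: 8 years of follow-up. Assumed: annual rate *s* of starting Cimzia among comparator patients; share *q* prevalent at enrollment, equal in both cohorts; Cimzia stopped at 0.5 per year; up to 2 years counted per late start; hazard doubled or quadrupled in the first 6 months.

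- Drop-out hazard: d = −ln(0.92) = 0.0834. Exit hazard on Cimzia: h = 0.0834 + 0.5 = 0.5834.
- Late Cimzia starts: N = 1674 × s/(s + d) × (1 − exp(−8(s + d))). For s = 1%, 3%, 5%, 10% this gives 94, 264, 412, 702.
- These starts inherit the enrollment label. At s = 5% and q = 25%, 50%, 75%, 103, 206 or 309 are filed as prevalent and 309, 206 or 103 as incident.
- Years per person, (1 − exp(−hT))/h: 0.434 for T = 0.5, 1.180 for T = 2, 1.698 for T = 8.
- Share of prevalent-stratum Cimzia time that is the first 6 months after a late start: 0.434N/(1.180N + 1.698 × 1371); *q* cancels. At s = 5%: 178.5/(485.9 + 2328.0) = 6.3%. For the four rates: 1.7%, 4.3%, 6.3%, 9.6%.
- Rate increase = share × (hazard multiple − 1). Doubled hazard: about 2% to 10%. Fourfold hazard: 5% to 29%.

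**Step 4: allow for early time already in the stratum.** Prevalent Cimzia patients with under 6 months of prior use also carry early time into the study. If prior use is uniform over 0 to 12 months (assumed), half have on average 0.25 year left, or 0.125 year per patient, and 0.114 year after exits. At s = 5% with a doubled hazard, the rate relative to the same stratum without late starts is (1 + (0.114 × 1371 + 178.5)/2813.9)/(1 + 0.114/1.698) = 1.049, against 1.063 without this allowance. Across the four rates the increase becomes about 1% to 7%.

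**The case against.** Several objections have force.

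- *The label is sound before the first switch.* This stands. A reader might infer that the stratification cannot do its job at all. The documents do not support that; how much is lost depends on a switch rate they do not give.
- *Later Cimzia starts are not all filed as prevalent.* This stands. That too might be inferred, but the starts inherit the patient's label, and those by comparator patients incident at enrollment stay incident.
- *The new-user stratum is not shown to be biased.* This stands for Cimzia time. Cimzia time there comes from starts at or after enrollment, so omitting some later starts costs precision.
- *Not every move from comparator to Cimzia is a first start.* This stands. Prior Cimzia is prohibited in the comparator cohort, but SAP 3.4 lists it as an important deviation, Appendix 1 covers patients with Cimzia before consent who take a comparator on study, and returns to Cimzia can occur.
- *The illustration inflates only the Cimzia rate.* This stands. Comparator starts by prevalent patients raise the comparator rate in the same stratum, so part of the effect cancels in the contrast. No ratio can be computed from the documents. The study also ended on 28 August 2020 (SAP 2.3), so late enrollees had less than 8 years in which to switch.
- *An enrollment label matches covariates measured at baseline.* This is a fair argument for keeping the label, but then only with time before the first switch.

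That the analysis is descriptive and the definitions sit among secondary analyses limits the consequences. It does not make the rule classify correctly.

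**Conclusion.** The concern holds in limited form. The stratifier and the exposure agree until the first switch and can disagree afterwards. For patients prevalent at enrollment, new-drug time is then filed as prevalent, for Cimzia and comparator drugs alike. The undefined *treatment* leaves some patients in both strata or in neither.

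The effect on the Cimzia/Comparator contrast is unknown. The Cimzia rate in the prevalent stratum rises by roughly 2% to 10% under the assumed switch rates and a doubled early hazard, and by somewhat less once early time already in the stratum is counted. These figures rest on assumed switching, persistence, prevalent share and early hazard, and do not estimate bias in the ratio. The point merits correction because the rule misclassifies when followed as written and the repair is cheap.

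**What to change.** In SAP 4.5 and 8.1.5, define status per treatment episode of the current drug: incident if the first recorded dose of that drug is on or after enrollment, prevalent if that drug was taken before enrollment. Carry the status with the exposure records, so that it changes when the drug changes. Also state:

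- how Overlap time, or pooled Comparator time, is classed when one drug is new and another is not;
- how start dates imputed to the consent date under SAP 4.2 are handled, since the rule would otherwise count them as incident.

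If the enrollment label is kept, name the treatment it refers to, give a rule for patients who meet both definitions or neither, and restrict the stratified analysis to person-time before the first switch.

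The cost is one extra derivation from medication history already collected at enrollment (Protocol 4.8.1), with no new data collection. Under the episode definition a patient may appear in both strata over time, and the adjustment covariates remain those measured at baseline, which describe a year-3 start less well than a start at enrollment.
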